- Secondary outcome 3: What is the impact of the “Putting the Kitbags to work” programme on the **stress** (as measured by the “Stress in General” scale) of social workers and family support workers in teams randomly allocated to the intervention arm compared with social workers and family support workers in teams randomly allocated to the control arm? The outcome will be measured at month 6 and month 13 after intervention began.
- Secondary outcome 4: What is the impact of the “Putting the Kitbags to work” programme on the **number of sick days** taken by social workers and family support workers in teams randomly allocated to the intervention arm compared with social workers and family support workers in teams randomly allocated to the control arm from T1 to T13?

Foster carer outcomes:

- Secondary outcome 5: What is the impact of the “Putting the Kitbags to work” programme on the **self-efficacy** of foster and kinship carers supported by social worker teams randomly allocated to the intervention arm compared with foster carers supported by social worker teams randomly allocated to the control arm as measured? The outcome will be measured at month 6 and month 13 after intervention began. The population will be restricted to local authority employed foster carers only..

Design

Trial type and number of arms	Parallel multi-site cluster RCT (2 arms)
Unit of randomisation	Social Work Team (6-8 social workers)
Stratification variables (if applicable)	Local authority and team type (CIN+CP/CLA/Children with disabilities)

Participants

Oxfordshire County Council, the London Borough of Bexley, Haringey Council and Warwickshire County Council shall be participating in the trial.

Teams

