Children are clustered into sibling groups, households (e.g. with other children in foster care) and caseloads (i.e. a group of children have the same social worker) and social worker teams. Because of this clustering, observations within one group (sibling group, household etc) may be more similar with each other on various characteristics compared with observations in other groups violating the assumption of independence. When data is structured in this way, the estimation of the treatment effect remains unbiased but the standard errors may be misspecified, leading to problems with inference. To correct for this, standard errors will be clustered at the level of randomisation, the social worker team level, in line with WWCS statistical guidance. This also accounts for correlations between observations at lower levels of nesting.

Handling non-compliance

If CYP are transferred to another team (e.g. due to a change of status), it is possible that the team to which they are transferred was ineligible for participating in the programme or had a different intervention / comparator group allocation. If a social worker or family support worker changes teams, it is possible that their new team had a different intervention/ comparator allocation. For all our analysis, we will conduct intention to treat analysis where a CYP is considered as treated if they are / were supported by a social worker who is a member of an intervention team at the point they entered the sample (either at randomisation or when their case started), irrespective of their use of Kitbag.

Multiple Comparison Adjustments

We will adjust for multiple comparisons within the secondary outcomes using Hochberg's step-up procedure, as per WWCS statistical guidance.

Regression specification

For social workers, family support workers and foster carer outcomes:

$$Y_{ict13} = \beta_0 + \beta_1 D_c + \beta_{2:4} A_c' + \beta_5 Y_{ict0} + \beta_{6:k+6} X_i' + \beta_{k+6:k+11} M_c' + \epsilon_c$$

Where:

- Y_{ict13} is the dependent variable for individual i , team c at the end of the trial, $t13$. β_0 is the intercept
- D_c is the treatment variable
- A_c is a vector of the local authority fixed effects
- Y_{ict0} is the "pre" outcome of individual i in team c , at their "pre" data collection point, $t0$
- X_i' is an $N \times k$ matrix of characteristics of individual i
- M_c' is an $N \times 5$ matrix of characteristics of team c
- ϵ_c is the error term clustered at the team level c

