For child outcomes:

$$Y_{ict13} = \beta_0 + \beta_1 D_c + \beta_{2:4} A_c' + \beta_5 Y_{ict0} + \beta_{6:k+6} X_i' + \epsilon_c$$

Where all is defined as above.

Exploratory Analysis

Site effects

In line with WWCS statistical guidance, we account for potential site effects by including a site (local authority) fixed effect and interaction terms between the treatment and sites. The coefficients on these interaction terms can be interpreted as the difference in intervention group mean for that site and the overall treatment mean. The trial is not powered to detect site-specific effects, and so we report only the direction of the site-dosage effects and the standard errors as exploratory analysis. The interpretation of the coefficient on the treatment variable is the simple average between sites (rather than an average weighted by sample size at each site).

Site effects will be tested for all outcomes. The regression specifications will follow the above with the addition of a vector of interaction terms between treatment and local authority fixed effects. E.g. for social workers and foster carer outcomes:

$$Y_{ict13} = \beta_0 + \beta_1 D_c + \beta_{2:4} A_c' + \beta_{5:8} D_c * A_c' + \beta_9 Y_{ict0} + \beta_{9:k+9} X_i' + \beta_{k+9:k+14} M_c' + \epsilon_c$$

Where:

- $D_c * A_c'$ is a vector of interaction terms between treatment and local authority fixed effects.
- And all else is defined as above

Dosage

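### The exploratory site-effects equation does not give its coefficients the meanings the protocol assigns to them, because the authority coding those meanings need is not stated

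*Protocol*

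**What the plan says.** The Participants section names four authorities: "Oxfordshire County Council, the London Borough of Bexley, Haringey Council and Warwickshire County Council shall be participating in the trial". In the Regression specification the authority term "is a vector of the local authority fixed effects", with coefficients numbered 2 to 4, so three columns beside an intercept.

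Under Exploratory Analysis, Site effects, the example equation keeps the intercept, the treatment term and the three authority terms. It then adds interactions with coefficients numbered 5 to 8, which is four. The added term "is a vector of interaction terms between treatment and local authority fixed effects". Two sentences tell the reader what the coefficients mean:

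- for the interactions: "The coefficients on these interaction terms can be interpreted as the difference in intervention group mean for that site and the overall treatment mean";
- for the treatment term: "The interpretation of the coefficient on the treatment variable is the simple average between sites", explicitly not a mean weighted by site size.

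On output, the section says "we report only the direction of the site-dosage effects and the standard errors as exploratory analysis". The Reporting list repeats direction and standard errors for the site-treatment effects. The model is to be run for all outcomes. No coding for authority is stated in the section.

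**The concern.** The protocol fixes both an equation and a reading of its coefficients, and the two do not agree. The reading describes deviation coding. The equation, with one authority omitted from the main effects and an intercept retained, looks like ordinary indicator coding, which gives the coefficients different meanings.

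The output promised for this model is the direction and standard error of the site effects, and both depend on the coding. An analyst who enters authority as an ordinary factor would obtain signs relative to one arbitrary authority, and the protocol's text would present them as signs relative to an average.

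**Working it through.** **Inputs.** Four authorities (Participants). Teams per authority: Bexley 9, Haringey 11, Oxfordshire 30, Warwickshire 10, total 60 (Table 1). Coefficient numbering from the Site effects equation. Assumed for illustration only: true effects τ of 0.1, 0.2, 0.3 and 0.8 in that order. Their simple average is 1.4/4 = 0.35. The team-weighted average is (0.9 + 2.2 + 9.0 + 8.0)/60 = 0.335. The protocol gives no figure of its own to reproduce.

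**1. Literal reading, four interactions.** The site part has 1 + 1 + 3 + 4 = 9 columns. The authority indicators sum to 1, so the four treatment-by-authority columns sum to the treatment column and the rank is 8. Adding any constant to β1 and subtracting it from all four interactions leaves the fit unchanged, so β1 is not identified. A minimum-norm solver returns 1.4/5 = 0.28, which is neither the average nor any authority's effect.

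**2. Three indicator interactions** (also the result when software drops one interaction). Rank is 8 of 8. With reference authority r, β1 = τ_r and each interaction is τ_k − τ_r. So β1 is 0.1, 0.2, 0.3 or 0.8 according to the reference, and never 0.35.

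**3. Sum-to-zero coding, three interactions.** Rank is 8 of 8, β1 = 0.35, and the interactions are −0.25, −0.15 and −0.05, with the fourth implied as +0.45. Both stated meanings hold. Centring three indicators at 1/4 also gives β1 = 0.35, but the interactions stay contrasts with the reference authority (0.1, 0.2, 0.7), so only the first meaning holds. Centring at sample shares gives 0.335, the weighted mean that the protocol disclaims.

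**4. Effect on reported directions.**

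| Authority | Assumed effect | Deviation from 0.35 | Contrast with Bexley | Contrast with Warwickshire |
|---|---|---|---|---|
| Bexley | 0.1 | −0.25 | reference | −0.7 |
| Haringey | 0.2 | −0.15 | +0.1 | −0.6 |
| Oxfordshire | 0.3 | −0.05 | +0.2 | −0.5 |
| Warwickshire | 0.8 | +0.45 | +0.7 | reference |

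With Bexley as reference, Haringey and Oxfordshire change sign. With Warwickshire as reference, no sign changes. A reversal is therefore possible but not certain.

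**5. Effect on standard errors** (illustrative; equal team sizes and a 50:50 split within each authority). The variance of an authority's effect is proportional to 4/J: 0.444, 0.364, 0.133, 0.400. The variance of the simple average is 1.341/16 = 0.0838. The ratio of the standard error of one authority's effect to that of the average is √(0.444/0.0838) = 2.30, then 2.08, 1.26 and 2.18.

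The interactions change too. Oxfordshire's deviation has variance (9/16)(0.133) + (0.444 + 0.364 + 0.400)/16 = 0.150. Its contrast with Bexley has 0.133 + 0.444 = 0.578. The standard errors differ by a factor of √(0.578/0.150) ≈ 1.96.

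**The case against.** **The stated meanings may themselves show the intended coding.** Both sentences fit sum-to-zero coding, and contrast coding is often left to the SAP or the code. This stands in part: the protocol does not exclude that coding. But it does not state it, and its practice elsewhere points the other way. Categorical covariates are given reference categories. The interaction models for type of social care involvement and for age count terms as categories minus one (five categories and four terms; four categories and three terms), and the former is correctly read against the reference group.

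**The four-term count may be a slip.** This largely stands. Treatment multiplied by a three-column vector gives three terms. Compared with the main equation, the individual covariates start at 9 instead of 6 and the team covariates at k+9 instead of k+6, which is the shift three interactions would produce; only the baseline outcome moves by four. One index is used twice in this equation and in the dosage equation. Four deviations under a sum-to-zero constraint would also be identified. The mismatch does not depend on the count, however, because three indicator interactions fail to give the stated meanings as well.

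**Stronger readings.** A reader might infer that the trial will report one authority's effect as its overall result. The documents do not support that. The omitted-authority result depends on indicator coding, and this model's treatment coefficient is not on the reporting list. The Covariates section also says that the primary and secondary models carry no site-treatment interactions. If the authors meant the sign of each authority's own effect, coding would not matter, but the section interprets only the interactions and the treatment coefficient.

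**The standard-error ratios are soft.** This stands. Table 2 lists 119 intervention-group staff in Warwickshire against 120 in Oxfordshire, with 10 and 30 eligible teams, so equal team size is doubtful. For staff outcomes, using the Table 2 counts, half the teams per arm, a mirrored control arm and the children's ICC of 0.03, the ratios are about 2.4, 2.5, 1.3 and 1.5.

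**Conclusion.** The equation and its interpretation need to be reconciled. As printed the model is rank-deficient. Read with three indicator-coded interactions, it is estimable but gives the reference authority's effect and contrasts with that authority. Only a coding the protocol does not state gives both meanings it claims. That rank result and those identities are algebra and rest on no assumption about the data.

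The size of the practical effect does rest on assumptions. The sign reversals come from invented site effects and one choice of reference authority. The ratios of about 2.3, 2.1, 1.3 and 2.2 need equal team sizes and even allocation within each authority.

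Separately, under any coding the interactions are differences in treatment effect. The protocol's sentence describes them as differences in the mean outcome of treated participants, which is a different quantity.

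The point is worth correcting before analysis because the affected quantities are the ones to be reported. Its reach is limited to this exploratory analysis.

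**What to change.** Write the site part as β0 + β1 D + Σ α_k S_k + Σ γ_k D S_k for k = 1 to 3, where S_k is 1 in authority k, −1 in the fourth authority and 0 otherwise. Then β1 is the unweighted mean of the four effects and γ_k is authority k's deviation. The fourth deviation is −(γ1 + γ2 + γ3), with its standard error taken as a linear combination from the team-clustered covariance matrix.

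Equivalently, estimate the four authority-specific effects and report their unweighted mean and each deviation with its standard error as contrasts.

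Correct the coefficient numbering, describe the interactions as differences in treatment effect, and say that the reported directions are relative to the unweighted mean. The cost is a revised equation, two reworded sentences and one line of code. It needs no extra data and does not touch the primary or secondary analyses.

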Local authority	Number of social workers and family support workers in teams in the intervention group	Hold back for staff turnover (assume 15%)	Number of foster carers (including kinship carers) in the intervention group	Hold back for new foster carers (assume 10%)	Number of Kitbags for social workers in the fostering service	Total
Bexley	33	5	57	6	2	103
Haringey	28	4	100	10	2	144
Oxfordshire	120	18	119	12	4	273
Warwickshire	119	18	148	15	10	310
Total	300	45	424	43	18	830

Children and young people

Children and young people aged 4-18 years old who have an open case in May 2021 or whose case opens between May 2021 and December 2021 and supported by social workers and family support workers in eligible teams are eligible for the programme. Only those whose

case starts before December 2021 will be eligible to allow for the minimum number of sessions to feasibly be delivered with a Kitbag before the evaluation period concludes (May 2022).

The number of children and young people who are classified as children in need (according to the Department for Education’s broad definition including children on a child in need plan, child protection plan and children in care) across these four local authorities is approximately 13,000. We estimate that there are approximately 9300 eligible children and young people across the four local authorities (henceforth we refer to them as the population).⁶

Table 3: Number of children in need in Bexley, Haringey, Oxfordshire and Warwickshire between 2019 and 2020

Local authority	Number of children in need at 31 March (2019)	Number of children in need at 31 March (2020)
Bexley	1594	1757
Haringey	2073	2284
Oxfordshire	4511	4750
Warwickshire	3914	4073
Total	12092	12864

Recruitment

Social workers / family support workers

Social workers will be identified from their membership in eligible teams, as per the HR IT systems of the local authorities. The social workers and family support workers will be asked to provide their informed consent before participating in the primary data collection (survey, interviews). They will also be notified of the use of their absence data in the email inviting them to participate in the survey at T6 (prior to the data sharing) and of their rights in relation to the processing.

Children and young people

Children and young people will be identified as eligible by their allocation to a social worker in an eligible team.

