As represented in the logic model, one of the hypothesised mechanisms is carer self-efficacy. We measure parental / carer self-efficacy - “the parents’ beliefs about their effectiveness in overcoming or solving specific parenting problems” - using the parental self-efficacy subscale of the “Me as a parent” scale. The subscale consists of 4 questions and has been validated for parents of children aged 6 months to 15 years old. The subscale has good internal reliability (Cronbach’s alpha of .75), good test-retest reliability (.73), and good convergent validity (Pearson $r = .63$, $p.001$ between the 4 items of the MaaP self-efficacy subscale and the 8 items of the efficacy subscale of the 17-item Parent Sense of Competence scale²⁰). The questions will be adapted to account for those in non-parental caring roles. The population will be restricted to local authority employed foster carers only as these are the foster carers whom we will be able to access.

Analysis plan

Primary and Secondary Analysis

Primary analysis estimates the impact of the programme on our primary outcomes, whilst secondary analysis estimates the impact of the programme on our secondary outcomes. As the approach is the same, we outline it jointly below.

Models

The dependent variables are continuous and we will use an OLS regression. The regression coefficient on the treatment variable is interpreted as the impact of the intervention on the dependent variable (in the units described in the “Outcomes” section). Please see the “Outcomes” section for the expected direction of the impact.

¹⁸ Yankelovich, & Broadfoot, & Gillespie, Michael & Guidroz, Ashley. (2012). The Stress in General Scale Revisited: A One-factor Structure.. *Stress and Health*. 28. 137-148. The items (p.144) are Demanding, Pressured, Calm (R), Many things stressful, Nerve-wracking, Hassled, More stressful than I’d like, Overwhelming where (R) means reverse coded.

¹⁹ The Scale is usually calculated as the sum; however, we use the mean to allow for non-response.

²⁰ Hamilton, V. Matthews, J. & Crawford, S. (2014). Development and Preliminary Validation of a Parenting Self-Regulation Scale: “Me as a Parent”. *Journal of Child and Family Studies*. 24. 10.1007/s10826-014-0089-z.

Independent variable of interest: treatment

For the outcomes of social workers, family support workers and foster carers, treatment is coded as a binary variable where treatment = 1 if:

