Although the total intervention period lasts for 12 months, children and young people enter and leave services throughout the year with an estimated 50% of children and young people at T0 having left services by T13. Because of the extent of the dropoff and because an insight into the impact of the number of sessions Kitbags are used may affect future planning of how Kitbags are used in direct work, we considered it important to analyse the “dosage” of the treatment (where number of months of exposure is taken as a proxy of the number of sessions). Thus for CYPs’ and parents’ / carers’ outcomes (which are collected at the same time as the child’s), we have four possible “dosages” of the treatment: 0 months (control), 0-4 months, 4-8 months and 8-12 months. We test whether the programme affects the duration of the interaction with children’s social care (end date - start date) by regressing the duration of interaction with children’s social care on the independent variables defined in the regression specification above. If the coefficient on the treatment dummy is insignificant, we can be less concerned that the impact of the treatment is determining dosage and we code the treatment variable for the children and young people’s outcomes and the parent / carers’ outcomes as categorical:

- 0: control
- 1: 0-4 months’ treatment
- 2: 4-8 months’ treatment
- 3: 8-12 months’ treatment

The control condition (coded as 0) will be the base category, and so the coefficient on each of the dosages of the treatment can be interpreted as the impact of 0-4 months / 4-8 months / 8-12 months of the treatment on the outcome compared to control.

Dosage will only be tested for child and parent / carer outcomes as the dosage is likely to vary much for them than social workers and family support workers:

$$Y_{ict13} = \beta_0 + \beta_{1:3} D_c' + \beta_{4:6} A_c' + \beta_7 Y_{ict0} + \beta_{7:k+7} X_i' + \epsilon_c$$

Where:

- D_c is a vector of treatment dosages
- And all else is defined as above

Impact on CYP with different levels of CSC involvement

It may be that there is a differential impact for CYP depending on the type / extent of social care involvement (if the child is on a child in need plan or a child protection plan or whether they are looked after). We add an interaction term of treatment and most recent type of CSC intervention at the start of the intervention period:

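### The check that lets the dosage analysis proceed tests a duration that is undefined for open cases and includes pre-trial time, so a non-significant result is weak reassurance

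*Protocol*

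**What the plan says.** The Protocol, under Exploratory Analysis, Dosage, groups treated children by 0–4, 4–8 and 8–12 months of treatment, where "number of months of exposure is taken as a proxy of the number of sessions". The stated reason is turnover, with "an estimated 50% of children and young people at T0 having left services by T13".

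The section first tests whether the programme changes the length of involvement. It defines the variable as involvement with children's "social care (end date - start date) by regressing the duration of interaction with" children's social care on the variables of the main specification. The rule that follows is: "If the coefficient on the treatment dummy is insignificant, we can be less concerned that the impact of the treatment is determining dosage". Treatment is then coded by dosage band, and each band's coefficient is read as the effect of that many months against control.

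Four other places bear on this:
- Participants, Children and young people: eligible children are those "who have an open case in May 2021 or whose case opens between May 2021 and December 2021".
- Analysis plan, Models: "The dependent variables are continuous and we will use an OLS regression".
- Standard errors: "standard errors will be clustered at the level of randomisation, the social worker team level".
- Missing data strategy, Outcomes: where missingness does not depend significantly on treatment, only observed outcomes are analysed. Otherwise outcomes are multiply imputed within arm.

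The Protocol does not say what end date a still-open case receives, and it does not tie the start date to entry into the sample.

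**The concern.** The check is meant to protect a 0–12 month exposure variable, but the duration it tests differs from that variable in two ways.

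1. **No end date.** On the Protocol's own estimate, about 100% − 50% = 50% of T0 children are still open at T13. Least squares on an end-minus-start variable has no value for them. Keeping only closed cases conditions on closure, the very event whose timing is in question.
2. **Start before the trial.** As an illustration, a child in care since 2016 whose case closes in July 2021 scores more than five years, of which about two months could reflect Kitbag. The same child with a case still open scores nothing. A case open from June to August 2021 scores two months.

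Closure is a level of the primary outcome, and a reduction in involvement is counted as a benefit. An effect of treatment on time in services is therefore plausible. If the check misses it, the bands are reported as effects of more or fewer months when treatment itself helped decide who falls in which band.

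**Working it through.** **Figures in the plan.** The only relevant one is the 50% leaving by T13. It is given without inputs and cannot be re-derived. No power is stated for this check.

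**Signal lost by keeping closed cases.** Assume a constant closure rate with 50% of controls closed at 12 months: λ = ln 2 / 12 = 0.0578 per month. With 25% faster closure, λ = 0.0722 and the share still open at 12 months is 0.5^1.25 = 0.420.

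- Mean time in services within 12 months, (1 − e^(−12λ)) / λ: control 0.5 / 0.0578 = 8.66; treated 0.580 / 0.0722 = 8.03. Difference 0.63 months.
- Mean among cases closed by 12 months, 1/λ − 12S/(1 − S), where S is the share still open: control 17.31 − 12.00 = 5.31; treated 13.85 − 8.71 = 5.14. Difference 0.17 months.
- Share of the signal lost: 1 − 0.17/0.63 = 73%.

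**Role of pre-trial time.** For a case open at T0, end minus start equals time open before T0 plus time in the trial. The first part is balanced in expectation by randomisation, so with all cases retained it adds variance rather than bias. If time open at T0 is a covariate, the treatment coefficient for the total equals the coefficient for in-trial time with the same covariates.

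**Power by simulation.** Both sets use 60 teams of 150 children (the Protocol's sample size table), constant closure rates and a two-sided 5% test. The other inputs are assumptions.
- Set A: 30% of children enter after the start; mean pre-trial case length 12–24 months; SD of the log team closure rate 0.15–0.30; least squares with team-clustered standard errors. Its covariate version adds months open at T0 and a new-entrant indicator.
- Set B: 40% enter later, evenly over 7 months; mean pre-trial length 12 or 36 months; SD 0.2; t-test on team means; 300 runs per setting (Monte Carlo error up to about 6 points).

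| Duration used | A: 25% faster | A: 50% faster | B: 20% faster | B: 50% faster |
|---|---|---|---|---|
| Closed only, from case start | 6–9% | – | 5–9% | 8–14% |
| Closed only, pre-trial time removed (covariate in A, counted from entry in B) | 28–38% | 79–88% | about 19% | 81–84% |
| Open cases capped at T13, from case start | 14–50% | 48–98% | 8–32% | 30–92% |
| As above, with time open at T0 as covariate | 68–100% | 100% | – | – |
| Entry to closure, capped at T13 | 72–99% | 100% | 83% | 100% |

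A dash means that no figure is given. Rejection rates with no effect were near 5%. The first and third rows are the most sensitive to the assumed pre-trial case length: shorter histories raise them.

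**The case against.** The strongest objection is that the check is less blind than a literal reading suggests. The regression uses the main specification, which contains a pre-measure of the outcome, and the Protocol expects previous values for administrative data. For duration, the natural pre-measure is time already open at T0. It removes the pre-trial noise, and if open cases are also capped at T13 the power matches that of the proposed definition. This stands as a possible reading, but the Protocol neither names that pre-measure nor states the cap. With the pre-measure alone, closed-only power is still 28–38% for 25% faster closure.

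A second objection is that faster closure would show elsewhere. The primary outcome counts closure as a de-escalation, and the cost evaluation estimates movements between levels. A simple closed-by-T13 indicator had 72–100% power for 25% faster closure. So this regression is not the only place where such an effect could appear. However, the Dosage section makes its decision on this regression alone.

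Third, if the missing-outcome rule applies to duration, missingness that differs by arm leads to imputation. That helps, but it does not stop the dosage coding.

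Finally, date derivations often belong in a statistical analysis plan. Here, though, the Protocol itself writes out the variable and the decision rule, and the variable does not match the exposure it is meant to protect.

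**Conclusion.** The point holds as a weakness of an exploratory analysis. As defined, duration is missing for about half of the T0 children and carries pre-trial time for cases already open. For 25% faster closure, power is about 6–9% on the literal reading, about 28–38% with time open at T0 as the pre-measure, and about 72–99% for in-trial time capped at T13. These figures rest on constant closure rates and on assumed pre-trial case lengths, team variation and share of new entrants. The 50% refers to children present at T0, and the Protocol gives no split between open and new cases.

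A reader might infer more than the documents support:
- That the check cannot see any effect on duration. With open cases capped at T13 it is weakened without the pre-measure and adequate with it. Even closed-only analysis with the pre-measure reaches 79–88% for 50% faster closure.
- That pre-trial time biases the arm comparison. Where all cases are kept, it adds noise.
- That primary or secondary estimates are affected. They do not depend on this check.
- That a better check would make the dosage result causal. Each treated band is still compared with all controls, and short-stay and long-stay children may differ from controls for reasons other than Kitbag.

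**What to change.** Replace the end-minus-start definition with: months from the child's entry to the sample (May 2021, or case opening if later) to case closure, with cases still open counted to T13. Later entrants have shorter maximum follow-up, so include month of entry in the model. Alternatively, use a Cox model with team-clustered standard errors and censoring at T13. Report the estimated effect on duration with its confidence interval, so that readers can see which effects on dosage are excluded rather than relying on non-significance. Keep the band-versus-control coefficients labelled as non-causal.

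The cost is a sentence or two in the analysis plan. Sample entry is already defined under the treatment variable, and status and closure data are already requested for the primary outcome, so no new collection is expected.
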